This is a prospective cross-sectional observational project, with no intervention. Observational exercise testing will include endurance exercise and muscle strength. Patients participating in this study will be treated according to current guidelines (ATS/ERS/ WASOG). As such, diagnostic procedures or treatment will not be postponed or impacted on by participation in this study. All data will be self-reported and self-referred for voluntary participation. Participants will be invited to attend the laboratory for testing on two occasions to measure physical activity, fatigue, aerobic fitness and muscular strength with exercise testing at the Human Performance lab, Kingston University, London to establish the influence on symptoms, physiological and psychological outcomes. Exercise testing will follow standard guidelines (ACSM, 2016). Travel cost reimbursement will be offered to all participants who attend lab visits.

Appropriate health and risk stratification screening will be performed via a submaximal exercise screening form (appendix XI) and any participant with an injury in the past 6 months or a known contraindication (ACSM, 2014) to exercise will be excluded from the study. Inclusion criteria are based on having pulmonary sarcoidosis, aged 18 years or above, and participants may have other forms too but must have pulmonary sarcoidosis.

1. During the two laboratory visits to the Human Performance Lab, patients reported response will be objectified by three standardized questionnaires (IPAQ, SHQ and FAS), pulmonary function tests, mass and stature laboratory data will be recorded.

2. The patient is asked to keep a daily record physical activity by wearing a triaxial accelerometer on their hip to measure daily physical activities and ambulatory movements for 7 days.

Lab Procedures

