During visit one, participants will sign informed consent forms (appendix II) and have any questions answered before continuing. They will then be put through a screening process beginning with physical examination: characteristics such as anthropometric data (stature, mass, heart rate (HR), blood pressure, age, BMI, fat% (Bodpod, Cosmed/ Bioelectric Impedance Analysis (BIA), Tanita) will be collected. Following this, participants will conduct a lung function test via computer spirometery (Oxycon Pro, VIASYS GmbH, Eric Jaeger, Hoechberg, Germany), their predicted results will be corrected for ethnicity (Bellamy, 2005) allowing an accurate percentage of lung function to be recorded. Caucasian results remain the same, whilst Black-Caribbean are decreased by 13% (Bellamy, 2005). Participants will then conduct muscle strength testing of key muscle groups using an isokinetic dynamometer (Biodex System 4, Biodex Corporation, NY, USA); tests include: elbow flexor muscle strength (EFMS), quadriceps peak torque (QPT) and hamstring peak torque (HPT). In addition to this handgrip strength will also be assessed via handgrip digital dynamometer (Accord Medical Products). A minimum rest period of 20 minutes will follow (Vainshelboim et al., 2014) based on exercise-based pulmonary rehabilitation research. Heart rate (bpm) will be checked at the end of this period and in two minute intervals until HR returns to baseline as per ACSM (2014) guidelines. Physical testing will not take place until this return to baseline. Following this rest period participants will conduct a sixminute walk test (6MWT) during the test participants will be measured for Borg rate of perceived exertion and Borg Dyspnoea at 2 minute intervals and at completion of the test and oxygen saturation levels of participants will be recorded during the 6MWT via a portable pulse oximeter. Once the 6MWT has been completed participants will complete three guestionnaires, the fatigue assessment scale (FAS; De Vries et al., 2004), international physical activity questionnaire (IPAQ; Ekelund et al., 2003) and Sarcoidosis Health Questionnaire (SHQ; Cox et al., 2003). Before leaving, participants will be given tri-axial accelerometers (GT3X+ accelerometer, Actigraph), which will be used to measure the participants physical activity (PA) for seven days, to establish habitual physical activity levels and compare against the results of the IPAQ.

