During the second lab visit, participants will return their accelerometers and follow the same pattern of testing from the first visit, excluding the questionnaires (SHQ, FAS & IPAQ) and anthropometric information. The order of testing will follow ACSM (2016)

guidelines therefore strength and aerobic/anaerobic capacity will be first. Alongside this, age-matched healthy participants with no known interstitial lung disease (ILD) or other condition linked to reduced physical activity will used as a comparison between sarcoidosis and healthy populations.

Statistical analysis

A mixed model repeated measures analysis of variance (ANOVA) will be utilized, in addition to correlations and regressions.

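### No scheduled IPAQ covers the seven accelerometer days, so a last-7-days form would share no days with the record it is compared with

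*Combined protocol and SAP*

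**What the plan says.** The Aim and Primary Outcome paragraphs make the contrast between perceived activity (IPAQ) and actual daily activity the main object of the study.

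Lab Procedures gives the order of events:

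- Visit one: "Once the 6MWT has been completed participants will complete three guestionnaires", of which the IPAQ is one. After that, "Before leaving, participants will be given tri-axial accelerometers", worn for seven days "to establish habitual physical activity levels and compare against the results of the IPAQ".
- Visit two: "participants will return their accelerometers and follow the same pattern of testing from the first visit", "excluding the questionnaires (SHQ, FAS & IPAQ) and anthropometric information".

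Item 1 under Experiment Design is looser: "During the two laboratory visits to the Human Performance Lab, patients reported response will be objectified by three standardized questionnaires". The same sentence adds that "mass and stature laboratory data will be recorded".

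Statistical analysis names a mixed-model repeated measures ANOVA "in addition to correlations and regressions". Participants sets a target of 15, calls the study a pilot, and says the evidence does not allow accurate power calculations.

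The available text does not state the IPAQ form or its recall period (an appendix not supplied may do so), or how long after the last worn day visit two takes place.

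**The concern.** A comparison of reported with measured activity isolates reporting error only when both refer to the same period. Here the report is given before the first recorded minute. With a last-7-days form, the primary comparison mixes two things: how well people report, and how much their activity really changed from one week to the next. The planned correlations and regressions would be attenuated, and a weak association could be read as poor self-report when it partly reflects a different week. Because the study is a pilot for a larger trial, that ambiguity could carry forward. No later analysis can recover a worn-week report that was not collected.

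**Working it through.** **Does Experiment Design item 1 supply a second IPAQ?** It names both visits and three questionnaires in one sentence, but it also lists mass and stature. Lab Procedures drops the anthropometric measures at visit two as well as the questionnaires. Item 1 therefore reads as a list pooled over the two visits, and the explicit visit-two exclusion governs.

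**Overlap in days (visit one = day 0), assuming a last-7-days form.** Recall covers days -7 to -1. Wear covers days 0 to 6 or 1 to 7. Shared days: 0 of 7 either way. If the visit day is counted in both periods, one calendar date is shared, but the form is completed before the device is issued, so no recorded time is shared.

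**The plan's own figure.** The target of 15 cannot be reproduced, because no effect size, SD or correlation is given. The power results below are illustrations and do not test that target.

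**Model.** Weekly activity = U + e, with Var(U) = ρ, Var(e) = 1 − ρ and total variance 1, so ρ is the week-to-week correlation of true activity. Report = activity in its reference week + independent error of SD s. The documents give neither ρ nor the report accuracy. Assumed: ρ = 0.9, 0.7 or 0.5, and a same-week report correlation of 0.7, which gives s = √(1/0.49 − 1) = 1.020.

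- Correlation of the visit-one report with the worn week: 0.7 × ρ.
- Slope of measured on reported: ρ/(1 + s²) = 0.49 × ρ.
- SD of the paired difference: √(s² + 2(1 − ρ)), against s when the weeks match.
- Power: simulated t test of r, n = 15, two-sided P<0.05 (critical |r| = 0.514), 400,000 replicates.

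| | Same week | ρ = 0.9 | ρ = 0.7 | ρ = 0.5 |
|---|---|---|---|---|
| Expected correlation | 0.70 | 0.63 | 0.49 | 0.35 |
| Slope | 0.490 | 0.441 | 0.343 | 0.245 |
| SD of difference | 1.020 | 1.114 | 1.281 | 1.429 |
| Increase in SD | – | 9% | 26% | 40% |
| Power at n = 15 | 0.88 | 0.76 | 0.48 | 0.25 |
| n for 80% power | 13 | 17 | 30 | 61 |

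The increase in SD applies equally to the standard error of the mean difference and to the width of any limits of agreement. In a simulation of 1,000,000 people the mean difference stayed within 0.002 of zero.

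**Varying report accuracy (ρ = 0.9 / 0.7 / 0.5).**

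| Same-week correlation | Increase in SD | Power at n = 15: same week, then visit-one report |
|---|---|---|
| 0.3 | 1% / 3% / 5% | 0.19, then 0.17 / 0.12 / 0.08 |
| 0.5 | 3% / 10% / 15% | 0.50, then 0.41 / 0.25 / 0.15 |
| 0.9 | 36% / 89% / 129% | not computed |

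Whatever the report accuracy, the correlation and the slope are multiplied by ρ.

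**Usual-week form (U + error, s = 1.020).** The correlation with the worn week is ρ/√(ρ + s²) = 0.65 / 0.53 / 0.40, the same before and after wear. Timing loss: zero.

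**The case against.** The strongest reply is that the harm depends on something the available text does not settle. The stated purpose of the device is habitual activity, which fits a usual-week form, and then the order of form and device does not matter. Even a last-7-days report, if habitual activity is the target, correlates with U at 0.7 × √ρ = 0.66 / 0.59 / 0.49 whichever week it covers; part of the matched-week 0.70 is shared week-specific variation. This stands, and it is why the loss is stated as conditional. It does not remove the point: the primary outcome sets measured against reported activity and can equally be read as a same-week comparison, and the plan does not say which is meant.

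Second, the size depends heavily on report accuracy. This also stands: the increase in SD runs from about 1% to 129% over same-week correlations of 0.3 to 0.9. If self-report is poor, the timing adds little to the SD. The multiplication of the correlation by ρ is unaffected.

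Third, 15 people cannot separate these explanations well in any case. An observed correlation of 0.70 has a 95% Fisher interval of about 0.29 to 0.89, which contains 0.63, 0.49 and 0.35. That is fair: matching the weeks removes one explanation for a weak correlation but does not make the estimate precise.

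Fourth, a report given before wear is free of any influence of the monitor and is a defensible choice. That is a reason to keep it, and to say why, but not a reason to have no worn-week report.

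**Conclusion.** The concern holds and should be fixed. That no scheduled IPAQ covers the worn days follows directly from Lab Procedures and is held with high confidence. The consequence is conditional on a last-7-days form: 0 of 7 days shared, and correlation and slope multiplied by the week-to-week correlation of true activity (0.9 to 0.5 assumed). The mean difference becomes less precise but is not biased unless activity shifts systematically between the two weeks. The SD and power figures rest on assumed values and show scale only. With a usual-week form no timing loss is claimed; what remains is that the plan does not say so.

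**What to change.** 1. State the IPAQ form and recall period.
2. Remove the IPAQ from the visit-two exclusion. Give a last-7-days IPAQ at device return with the worn dates as its reference period, and name it as the comparator for the primary outcome.
3. Keep the visit-one IPAQ as the report of activity before monitoring.
4. State when visit two falls relative to the last worn day. With standard last-7-days wording in place of the worn dates, a 1-day gap leaves 6 of 7 days of overlap and a 3-day gap leaves 4 of 7. With day-level deviations assumed independent, the between-period correlation is ρ + (1 − ρ)(7 − d)/7 for a gap of d days. The expected correlation is then 0.69 / 0.67 / 0.65 for d = 1 and 0.67 / 0.61 / 0.55 for d = 3.
5. Align Experiment Design item 1 with Lab Procedures by saying which questionnaires are given at which visit.

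If a usual-week form is the intended comparator, say so and give the reason; the visit-one timing then needs no change.

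The cost is one questionnaire already in use, at a visit already scheduled, plus wording. The downside is that a week of wearing the monitor may alter perceived activity, and a worn-week report describes that week rather than habitual activity. The documents give no figure for the monitor effect. Comparing the two IPAQs is only a partial check on it, because a difference could also be a real change in activity.

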Physical activity has frequently been suggested as beneficial for sarcoidosis patients (NHS, 2015a). This is due to a host of specific and non-specific benefits to those with the condition. This includes the overall improvement to health including decreased levels of non-communicable diseases as well as lower the risk of depression (NHS, 2015b). Although anyone can suffer from depression, sarcoidosis patients have been shown to have increased levels (Hinz et al., 2012). In addition, physical activity helps not only to slow and stop deconditioning; a major issue within sarcoidosis (Fleischer et al., 2014), but also aids the reversal of this process (Strookappe et al., 2015). However, the condition lacks specific guidelines, unlike similar conditions such as COPD and asthma (ACSM, 2014; National Institute of Health and Care Excellence (NICE), 2016). Due to this, sarcoidosis patients are often given advice on exercise and other forms of physical activity such as walking or dancing that are not underpinned by research specific to their condition and as such are potentially dangerous exercise programmes/advice. Holland et al. (2015) states the unique presentation of ILD, including sarcoidosis, requires modifications of exercise prescription for individuals, which was noted as a key issue by Strookappe et al. (2016) in a systematic review of physical activity and training in Sarcoidosis. In addition to this, the effect of pulmonary sarcoidosis on exercise capacity and strength in comparison to a healthy population is limited and needs further research. Reductions to both exercise capacity and muscle strength indicated by lower results than normative values, are known primary symptoms of Sarcoidosis (Spruit, 2005; Hildebrand et al., 2012; Baughman, 2013),

which continue to get progressively worse with the onset of secondary symptoms such as deconditioning (Mitchell et al., 2012; Fleischer et al., 2014). The symptoms of sarcoidosis, in tandem with the varied manifestations (Skin, liver, heart etc. (Saidha et al., 2012)) of the disease alongside pulmonary, make it incredibly hard for accurate, suitable suggestions for physical activity, especially when considering the current lack of literature. This is highlighted by the role of fatigue within sarcoidosis, which is recognised as a major factor within the disease (Baughman, 2013) and therefore needs considering when creating an exercise prescription plan.

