Therefore, increased understanding of the effects of pulmonary sarcoidosis is needed as well as comparison to a healthy age matched control population to allow for the data to be compared alongside other intestinal lung diseases (ILD). Further research into this area is vital as exercise training has been shown to be in some cases just as/more effective than medical treatment across a wide range of chronic conditions (Pedersen & Saltin, 2015). Marcellis et al. (2013) argues rehabilitation should be utilised alongside any pharmacological treatment despite the need for future research on potential benefits. Strookappe et al. (2016) also states further random controlled trials are needed but the effects of physical training seem promising from the current limited research.

Despite Sarcoidosis affecting a significant number of people globally, being second only to asthma in young adults for respiratory diseases (Morgenthau & lannuzzi, 2011), there is a short supply of research into the condition as well as novel treatments to alleviate the primary and secondary symptoms. Therefore therapies (diet and physical activity) are required to help the condition but also prevent further reductions in QOL.

Aim: The primary aim of this study is to ascertain the physical activity patterns and baseline parameters in those with pulmonary sarcoidosis with regards to perceived physical activity and actual physical activity. The secondary aim of the study is to investigate the effect of pulmonary sarcoidosis in relation to muscle strength and exercise capacity against physical activity, lung function and oxygen saturation and how these differ from healthy normative values.

Primary Outcome: Daily physical activity measures against self-reported (IPAQ). **Secondary Outcome**: Demographic data and clinical status (age, gender & ethnicity); Body fat percent, Lung function (forced vital capacity), functional exercise capacity assessed by six-minute walk test, muscle strength by isokinetic dynamometer and hand dynamometer. Patient reported health status and pulmonary complaints objectified in disease-specific quality of life: Sarcoidosis Health Questionnaire and fatigue score (Fatigue Assessment Scale (FAS).

Participants

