Participants with medically diagnosed pulmonary sarcoidosis will be selected. They will be recruited through support groups and online forums from the known sarcoidosis population. A diagnosis of sarcoidosis will be accepted provided the participant has diagnosed pulmonary sarcoidosis ascertained by self-reporting. Patients will be prospectively recruited following new diagnosis of non-cardiac sarcoidosis. (1 in 10,000 have sarcoidosis of which 90% is pulmonary). Due to lack of research into sarcoidosis, there is not enough evidence to permit accurate power calculations, however, based on previous studies and the proportion of diagnosed cases, n=15 participants will be aimed for and act as a pilot for a larger randomised control trial (power 0.80 [80%], significance P<0.05) excluding drop-out.

Inclusion Criteria:

- Patients with known Sarcoidosis according to ATS/ERS/ WASOG criteria statement
- Age: 18-65 years Both males and females
- Written informed consent is obtained.
- Access to a computer with Internet

Exclusion Criteria:

- Contraindications to (not able to perform) physical tests or exercise testing - e.g. unstable cardiovascular disease, oncological, cardiac, neurological or orthopedic history making them unable to participate screened by a sub-maximal fitness screening form.

- An injury in the past 6 months that inhibits ability to perform exercise testing by a submaximal fitness screening form.

- Patients with a concurrent and predominant diagnosis of another significant respiratory disorder (for example: asthma, chronic obstructive pulmonary disease (COPD), cystic fibrosis, or lung cancer) by a sub-maximal fitness screening form.

- Pregnancy

- Physical disability (non-ambulatory patient e.g. wheelchair or bed-bound)

- Inability to obtain informed consent

- Cognitive failure making them unable to give consent or understand questionnaires or instruction.

Experiment Design

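### Controls are matched on age only and no sex term is committed, so the patient-control comparisons of strength and 6MWT distance are open to confounding by sex

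*Combined protocol and SAP*

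**What the plan says.** The comparison with healthy people is part of the study's stated purpose. The background says that evidence on "exercise capacity and strength in comparison to a healthy population is limited and needs further research", and the rationale asks for "comparison to a healthy age matched control population". The secondary aim concerns "muscle strength and exercise capacity against physical activity, lung function and oxygen saturation and how these differ from healthy normative values".

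- **Matching.** Lab Procedures (second visit) says that "age-matched healthy participants with no known interstitial lung disease (ILD) or other condition linked to reduced physical activity will used as a comparison". Age is the only matching factor. The number of controls, their source and the matching ratio are not given.
- **Eligibility.** Inclusion Criteria: "Age: 18-65 years Both males and females", with no quota by sex.
- **Data.** The secondary outcomes include "Demographic data and clinical status (age, gender & ethnicity", so gender will be available for analysis.
- **Design.** Experiment Design describes an observational cross-sectional study. Participants says that patients volunteer through support groups and online forums, with a target of 15.
- **Analysis.** The whole statement is: "A mixed model repeated measures analysis of variance (ANOVA) will be utilized, in addition to correlations and regressions". It names no covariate.
- **Scaling.** For lung function, Lab Procedures uses predicted values, and "their predicted results will be corrected for ethnicity". Nothing equivalent is stated for strength or walk distance.

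**The concern.** Where groups are randomised or matched on sex, leaving sex out of the model costs only precision. Neither applies here. Patients are self-selected, the source of the controls is unstated, and only age is aligned. If the two groups differ in their share of men, and men and women differ on the outcome, part of the patient-control difference is a sex difference. With fewer men among the patients and higher scores in men, a deficit appears that is not due to sarcoidosis. With the opposite mix, a real deficit is hidden. Recruiting more people does not remove this.

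Precision is a separate and lesser matter. Group and sex both vary between people. In a mixed ANOVA the group effect is tested against between-person variation, so repeating the tests at visit two does not take sex out of the error term.

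The outcomes at stake are muscle strength and 6MWT distance, and body fat if it is compared between groups. The primary outcome compares accelerometer and IPAQ within the same person and is not exposed in this way.

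**Working it through.** **Inputs from the documents.** Target n = 15, power 0.80, significance 0.05 (Participants); both sexes eligible; matching on age only; no sex term. The plan's n cannot be reproduced because no effect size or SD is given. Inverting a two-sided 5% t-test at 80% power gives a detectable difference of d = 1.06 if there are 15 v 15, or 1.57 if 15 is the total (8 v 7).

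**Assumptions not in the documents.** 15 controls unless stated; two-sided 5% test; within-sex SD = 1; male-female gap g = 0.5, 1, 1.5 or 2 SD; the sex mixes shown. The check compares a two-group model with and without a sex term. It uses one value per person and does not model the age matching. Simulation sizes are 100,000 to 200,000 trials per cell unless stated.

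**1. Bias when sex is omitted.** Bias = g × (male share in patients − male share in controls). The absolute size and the simulated false-positive rate are:

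| Men, patients v controls | Quantity | g = 0.5 | g = 1 | g = 1.5 | g = 2 |
|---|---|---|---|---|---|
| 5 v 10 | Bias = g × 5/15 | 0.17 | 0.33 | 0.50 | 0.67 |
| 5 v 10 | False positives, sex omitted | 6% | 10% | 14% | 17% |
| 4 v 11 | Bias = g × 7/15 | 0.23 | 0.47 | 0.70 | 0.93 |
| 4 v 11 | False positives, sex omitted | 9% | 18% | 30% | 42% |

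With sex in the model the estimate is unbiased and the rate is 5% in every cell. A milder split of 6 v 9 gives only 4 to 5% without sex, although the estimate still shifts by g × 3/15 = 0.10 to 0.40 SD.

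**2. How likely such splits are.** If both groups were drawn from a 50:50 population, the chance of a difference of 5 or more men is 0.0987, and the false-positive rate averaged over all draws stays at 5%. A systematic difference in sources raises the average: with true male shares of 30% v 50% and g = 1 it is 7.6% (20,000 trials).

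**3. Sample size does not help.** At 60 per group with 20 v 40 men and g = 1.5, the bias is still 1.5 × 20/60 = 0.50 SD, and the false-positive rate is 62% (20,000 trials).

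**4. Precision when the mix is similar.** At an exact 50:50 mix the SD without sex is inflated by √(1 + g²/4) = 1.03, 1.12, 1.25, 1.41. Averaged over 50:50 draws, which allows for the cost of estimating the sex effect, the mean 95% CI widths at 15 v 15 are:

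| g | Without sex | With sex | Ratio |
|---|---|---|---|
| 0.5 | 1.528 | 1.512 | 1.01 |
| 1 | 1.659 | 1.513 | 1.10 |
| 1.5 | 1.857 | 1.513 | 1.23 |
| 2 | 2.101 | 1.512 | 1.39 |

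The ratios are 1.01, 1.09, 1.22, 1.38 with 10 controls; 1.02, 1.10, 1.24, 1.40 with 30 controls; and 1.01, 1.08, 1.19, 1.33 with a 30:70 mix and 15 controls.

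**5. Precision when the mix differs.** The ordering can reverse. At g = 0.5 the unadjusted interval is about 3% narrower with 5 v 10 men (1.527 v 1.575) and about 9% narrower with 4 v 11 (1.521 v 1.678). It is then a narrow interval around a biased value.

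**6. Cost of adjusting if sex has no effect.** Over equal-mix draws, 1.512/1.483 = 1.02. For a fixed split with 15 men among the 30 people, the factor is 1/√(1 − r²), where r is the difference in male share. At 5 v 10, r² = 1/9 and the factor is 1.06. At 4 v 11, r² = 49/225 and the factor is 1.13.

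**The case against.** **The plan does not rule out sex.** The word regressions leaves room for a sex term, and gender is recorded. This stands, and it would be wrong to infer that the plan excludes adjustment. But nothing commits to it, and a one-clause commitment made before the data are seen is worth more than the option.

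**Normative values may handle it.** The secondary aim refers to healthy normative values. If these are sex-specific, that comparison is protected. The documents do not say so, and the direct comparison with recruited controls is a separate one.

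**The size rests on outside figures.** The sex gap, the sex mix and the number of controls are all assumed. At 0.5 SD the precision gain is negligible, and the documents cannot show where either outcome lies in the range. This stands; the figures are illustrations.

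**Why sex alone?** Stature, mass and BMI are also recorded and equally uncommitted. That is fair, but with about 15 patients a long covariate list is not affordable, and sex needs one degree of freedom.

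**It is a pilot and these are secondary outcomes.** True, and this limits the weight of the point.

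A reader might infer that the comparison is biased. The documents do not support that, because they report no sex mix for either group. Equally, a reader might take the issue to be lost precision only. That holds only if the sex mix is similar, which nothing in the design secures.

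**Conclusion.** The point holds as a risk of confounding by sex in the secondary patient-control comparisons of muscle strength and 6MWT distance, with lost precision as a second consequence. It follows from age-only matching, a non-randomised comparison, both sexes being eligible and no committed sex term. A marked imbalance at 15 v 15 could shift the difference by anything from about 0.2 to 0.9 SD; a mild one does little to the false-positive rate. All sizes depend on the assumed sex gap, sex mix and number of controls. Grade: cheap improvement.

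**What to change.** Extend the sentence under Statistical analysis to state that the patient-control comparisons of muscle strength and 6MWT distance include sex as a covariate, that the same applies to body fat if it is compared between groups, and that any normative values used are sex-specific.

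Where feasible, change the control description in Lab Procedures so that controls are frequency-matched on sex as well as age. Matching does not replace the covariate. It limits what adjustment costs and keeps both sexes represented in both groups, without which adjustment fails.

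The covariate needs no new data or visits and uses one degree of freedom. If sex turns out to have no effect on an outcome, the interval is about 2% wider on average with equal mixes, 6% at 5 v 10 men and 13% at 4 v 11. Matching on sex adds a constraint to control recruitment.

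### The primary IPAQ-versus-accelerometer comparison has no assigned method or unit, and the only scheduled IPAQ precedes the week that the accelerometer records

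*Combined protocol and SAP*

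**What the plan says.** The Aim paragraph reads "The primary aim of this study is to ascertain the physical activity patterns and baseline parameters in those with pulmonary sarcoidosis", qualified as "with regards to perceived physical activity and actual physical activity". The Primary Outcome is "Daily physical activity measures against self-reported (IPAQ"). Lab Procedures repeats the intent: the accelerometer data are collected "to establish habitual physical activity levels and compare against the results of the IPAQ".

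The Statistical analysis section is a single sentence: "A mixed model repeated measures analysis of variance (ANOVA) will be utilized, in addition to correlations and regressions". It attaches none of these methods to an outcome. No section names the IPAQ score, the accelerometer variable, a common unit or a wear-time rule. Nor does any section say whether the target is a mean difference, an association or individual agreement.

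On timing, Lab Procedures places the IPAQ at visit 1: "Once the 6MWT has been completed participants will complete three guestionnaires". The accelerometer is handed out after that, as the participant leaves, and is worn for seven days. At visit 2 the device comes back and testing is repeated, with the three questionnaires expressly left out. Experiment Design is looser: "During the two laboratory visits to the Human Performance Lab, patients reported response will be objectified by three standardized questionnaires (IPAQ, SHQ and FAS").

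On size, the Participants section says "n=15 participants will be aimed for and act as a pilot for a larger randomised control trial".

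**The concern.** The primary question is how perceived activity compares with measured activity, so the size of the gap is the result that matters. An unassigned list of ANOVA, correlation and regression leaves the authors free to report that the two measures are significantly correlated and do not differ significantly. That one statement is compatible with close agreement and with poor agreement, and a reader could not tell which.

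The schedule adds a second difficulty. If the visit 1 IPAQ asks about the preceding seven days, it describes one week and the device records the next. A discrepancy then mixes reporting error with real change between weeks, and the planned data offer no way to separate them.

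**Working it through.** **Plan's own figure.** n=15 is stated beside 80% power and P<0.05, but it cannot be reproduced. No effect size, SD, correlation, test or sidedness is given, and the Participants section itself says that an accurate power calculation is not possible. Working backwards (two-sided 0.05, 80% power), n=15 would detect a paired standardised difference of 0.78 or a correlation of 0.67. What the sample size means therefore depends on which method is primary, and the plan does not say. Below, n=15 is taken as 15 patients with complete data.

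**What the named methods yield.**
- Repeated measures ANOVA with instrument as a within-person factor gives the mean difference. Individual disagreement can be derived from its residual, since with two instruments SD of differences = √(2 × MSE). This needs a common unit and an instrument factor, and the plan specifies neither.
- Correlation gives association only.
- Regression gives intercept, slope and residual scatter. With equal SDs the residual SD is √(1−r²), whereas the SD of differences is √(2(1−r)). At r=0.7 these are √0.51 = 0.71 and √0.60 = 0.77. The residual is scatter about the fitted line and excludes mean bias.

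**Significance threshold for r at n=15.** With t(13, 0.975) = 2.160, r = t/√(n−2+t²) = 2.160/√(13+4.667) = 0.514.

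**Limits of agreement behind a given r** (assumed: equal SDs, zero bias; unit: between-person SD). Half-width = 1.96 × √(2(1−r)). The comparator is the 95% range for the difference between two people, 1.96 × √2 = 2.77.

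| r | Limits | Share of 2.77 |
|---|---|---|
| 0.514 | ±1.93 | 70% |
| 0.7 | ±1.52 | 55% |
| 0.9 | ±0.88 | 32% |

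**How often the uninformative statement would arise.** Simulated share of n=15 studies with a significant positive correlation and a non-significant paired t-test (200,000 bivariate normal samples per cell, equal SDs):

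| True r (assumed) | Zero bias | Bias 0.5 SD |
|---|---|---|
| 0.5 | 46% | 24% |
| 0.7 | 83% | 29% |
| 0.9 | 95% | 2% |

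With a bias of 1 SD every share is about 1% or less.

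**Precision of the proposed analysis at n=15**, in SD of the differences, with t(14, 0.975) = 2.145:
- Mean bias: 2.145/√15 = ±0.55.
- Each limit: 2.145 × √(1/15 + 1.96²/28) = ±0.97.

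**Timing.** The order of events in Lab Procedures is IPAQ, device issued, seven days of wear, device returned with no IPAQ. Suppose self-report were perfect and the week-to-week intraclass correlation (ICC) were 0.9 to 0.7 (assumed; the documents give no value). In SD of weekly activity:
- Report of an earlier week: 1.96 × √(2(1−ICC)) = ±0.88 to ±1.52.
- Report of a usual week: 1.96 × √(1−ICC) = ±0.62 to ±1.07.

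The second is smaller by a factor of √2.

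**The case against.** The aim is descriptive, the study is a pilot, and no section declares individual agreement as an objective. A group-level comparison may be all that is intended, and the confidence interval for the bias has no more power than the paired test of means. That stands as a reason to let the sponsor choose the target. It does not excuse leaving the target unstated.

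A reader might infer more than the documents support in four ways.

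- *That self-reports could be off by almost as much as people differ from each other.* This comes from setting ±1.93 SD beside ±1.96 SD, but ±1.96 SD is the spread of people about their mean. The range for the difference between two people is ±2.77 SD, so the ratio is about 70%, and only at the bare threshold of significance.
- *That the misleading statement is the likely result.* The high shares need a mean bias near zero. With a bias of 0.5 SD they drop to 24%, 29% and 2%, because the paired test then usually detects the bias.
- *That the named methods cannot show individual scatter.* Regression reports a residual SD, and the ANOVA residual can be converted. What is missing is a plan to report the disagreement itself.
- *That the schedule invalidates the comparison.* Lab Procedures describes the target as habitual activity. If the IPAQ asks about a usual week, neither measure is meant to be specific to one week and the effect is smaller. Asking before wear also keeps the device from influencing the answers. The recall period may be in an appendix that is not part of the supplied text.

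The Experiment Design sentence on questionnaires can be read as an overview of both visits. The explicit omission at visit 2 is the more specific statement, but the two passages should be made to agree.

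**Conclusion.** The concern holds in this limited form and should be acted on. Two facts rest on the text alone: no method or unit is tied to the primary comparison, and the only scheduled IPAQ comes before the wear week.

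The consequences are conditional. A just-significant correlation at n=15 can sit with limits of ±1.93 between-person SD, given equal SDs and no bias. How often the plan would end in an uninformative statement ranges from 95% of studies to almost none, depending on the true correlation and bias, which the documents do not give. The timing effect depends on the unstated recall period and on an assumed ICC. It mixes reporting error with week-to-week change if the recall is the last seven days, and matters less if it is a usual week. The documents do not support a claim that the primary comparison is invalid.

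**What to change.** **Analysis.** In patients, define the primary analysis as the within-person difference, IPAQ minus accelerometer, in one common unit such as minutes per day of moderate-to-vigorous activity. State the accelerometer cut-points and the valid-wear rule. Report mean bias with its 95% CI, and 95% limits of agreement with their CIs. If the spread grows with the mean, use regression-based limits, or ratio limits only if nobody records zero minutes. Keep correlation and regression as secondary, and use the mixed model for patient-control comparisons. If only a group-level comparison is wanted, say so and still report the bias with its CI and the SD of the differences.

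**Timing.** Give an IPAQ with last-7-days recall when the accelerometer is returned at visit 2, and use it for the primary comparison. Keep the visit 1 IPAQ as a secondary comparison, which would help to show whether wearing the device changes the answers. Reconcile the questionnaire wording in Experiment Design with the visit 2 text in Lab Procedures. If the IPAQ stays at visit 1 only, state its recall period and say that the limits include week-to-week variation.

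**Cost.** The analysis part is plan wording and a little more work on data already collected. The timing part is one more short questionnaire per participant at a visit already planned, plus a protocol wording change. The downsides are that device wear may influence the visit 2 answers, and that the limits will be imprecise at n=15 and more so after any dropout.
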